Appendix 6.	Protocol Amendment I8D-MC-AZEB(a) Summary Effect of LY3314814 on the Pharmacokinetics of Rosuvastatin in Caucasian Healthy Subjects.....	53

1. Protocol Synopsis

Title of Study:

Effect of LY3314814 on the Pharmacokinetics of Rosuvastatin in Caucasian Healthy Subjects

Rationale:

Rosuvastatin is a breast cancer resistance protein (BCRP; also known as ABCG2) substrate that is sensitive to BCRP activity in the gastrointestinal tract and liver. In vitro, LY3314814 has been characterized as a BCRP substrate and inhibitor. This study uses rosuvastatin as a substrate to evaluate whether LY3314814 is an inhibitor of BCRP activity in vivo.

Objectives/Endpoints:

Objectives	Endpoints

Primary
 
The primary objective is to evaluate the effect of LY3314814 on the pharmacokinetics (PK) of rosuvastatin in healthy subjects.
	
The primary endpoint is the area under the drug concentration-time curve (AUC) from zero to infinity (AUC[0-∞]) of rosuvastatin administered alone and with LY3314814.

Secondary
 
The secondary objectives are:
 
 • To assess the safety of LY3314814 when coadministered with rosuvastatin in healthy subjects; • To determine the effect of rosuvastatin on the PK of LY3314814. 	
Secondary endpoints include:
 
 • Incidence of treatment-emergent adverse events (TEAEs) and serious adverse events (SAEs); • PK parameters of LY3314814 administered alone and with rosuvastatin: C_{max}, t_{max}, and AUC during a 24-hour dosing interval (AUC_τ).

Summary of Study Design:

Study I8D-MC-AZEB is a Phase 1, open-label, fixed-sequence, 2-period crossover study in Caucasian healthy male subjects and female subjects not of childbearing potential. Healthy males and females are as determined by medical history, physical examination, vital signs, clinical laboratory tests, and safety electrocardiograms. Subjects are to be 18 to 65 years of age, inclusive, with a body mass index between 19 and 32 kg/m², inclusive, at screening. Subjects with c.34AA, c.421AA, or c.34GA/421CA as well as c.521TC and c.521CC genotypes will be excluded from this study. Eligible subjects must lack evidence of significant active or previous neuropsychiatric disease, assessed by medical history, physical examination, and Columbia-Suicide Severity Rating Scale (C-SSRS).

Treatment Arms and Duration:

Subjects will receive a single oral dose of 20 mg rosuvastatin on Period 1 Day 1. In Period 2, subjects will receive oral doses of 50 mg LY3314814 once daily on Days 1 to 12 with a single 20-mg rosuvastatin oral dose coadministered on Day 8.

Number of Subjects:

Up to 42 subjects may be enrolled in order that 24 subjects complete the study.

Statistical Analysis:

Pharmacokinetic: Rosuvastatin administered alone (Period 1 Day 1) will represent the reference treatment and rosuvastatin coadministered with LY3314814 will represent the test treatment (Period 2 Day 8) for rosuvastatin PK analysis. Pharmacokinetic parameter estimates will be evaluated to delineate the effects of LY3314814 on rosuvastatin PK. Log-transformed $AUC(0-\infty)$ and C_{max} estimates for rosuvastatin will be analyzed using a linear mixed-effects analysis of variance model with treatment as a fixed effect and subject as a random effect. The ratios of geometric least squares means (ie, rosuvastatin + LY3314814 to rosuvastatin alone) will be calculated along with the 90% confidence interval (CI) for the ratios. The t_{max} for rosuvastatin will be analyzed using a nonparametric method; median differences of rosuvastatin + LY3314814 to rosuvastatin alone and the 90% CI for the median of differences will be calculated. A similar analysis will be performed to evaluate the effect of rosuvastatin on LY3314814, where LY3314814 administered alone (Period 2 Day 7) will be the reference treatment and LY3314814 coadministered with rosuvastatin will remain the test treatment (Period 2 Day 8). Additional analysis may be conducted if deemed appropriate.

Safety: All investigational product and protocol procedure adverse events will be listed, and if the frequency of events allows, safety data will be summarized using descriptive methodology. The incidence of symptoms for each treatment will be presented by severity and by association with investigational product as perceived by the investigator. Each symptom will be classified by the most suitable term from the medical regulatory dictionary. The number of investigational product-related SAEs will be reported. Safety parameters that will be assessed include safety clinical laboratory parameters, vital signs, and C-SSRS. Orthostatic changes in vital signs will be assessed using change from supine to standing. The clinical laboratory parameters and C-SSRS data will be listed. Vital signs will be listed and summarized using standard descriptive statistics. Electrocardiograms will be performed for safety monitoring purposes and will not be presented. Additional analysis may be performed if warranted upon review of the data.

2. Schedule of Activities

Study Schedule Protocol I8D-MC-AZEB

Period 1

Procedure	Screening Up to 45 days prior to enrollment	Period 1							Comments
		Day							
		-1	1	2	3	4	5	6	
Outpatient Visit	X								
Subject Admission to CRU		X							
Informed Consent	X								
Medical History	X								
Height and BMI	X								
Weight	X	X							
Drug and Alcohol Tests	X	X							
C-SSRS	X	X							
Estimated GFR	X								Estimated GFR will be calculated using the CKD-EPI equation.
Physical Exam		X							After screening exam on Period 1 Day -1, exams are to include only medical review and targeted examination, as appropriate.
Pregnancy Test		X							Pregnancy tests will be performed for all females.
Vital Signs (supine and orthostatic) (hours) ^a	X		P, 4, 8, 12	24	X	X	X	X	Vital signs include blood pressure and pulse rate. Body temperature will be obtained at screening and as clinically indicated. Sampling times are relative to the time of rosuvastatin administration (0 hour). Additional vital signs may be measured during each study period, if clinically indicated.
Clinical Lab Tests	X	X						X	See Appendix 2 for details. Results from sample on Period 1 Day -1 will be reviewed by the investigator prior to dosing on Period 1 Day 1. Tests may be repeated at the investigator's discretion.
OATP1B1, OATP521 T/TT, and BCRP Genotypes	X								Genotypes will be used to confirm subject eligibility. Subjects who meet all other screening eligibility criteria will return for a second screening visit, at least 21 days prior to enrollment, when samples will be collected for genotype analysis.
12-lead ECG	X	X							Additional ECGs may be obtained as clinically indicated.
Genetic Sample			P						Single sample for pharmacogenetic analysis.

Procedure	Screening	Period 1							Comments
	Up to 45 days prior to enrollment	Day							
		-1	1	2	3	4	5	6	
Rosuvastatin Administration			X						
Rosuvastatin PK Samples (hours) ^a			P, 1, 2, 3, 4, 5, 6, 8, 12	24	48	72	96	120	Sampling times are relative to the time of rosuvastatin administration (0 hour).
Biomarker Samples (hours) ^a			P, 1, 2, 3, 4, 5, 6, 8, 12	24	48	72	96	120	Samples for non-pharmacogenetic biomarker analysis.
AE Assessment	X			X					

Abbreviations: AE = adverse event; BCRP = breast cancer resistance protein; BMI = body mass index; CKD-EPI = Chronic Kidney Disease Epidemiology Collaboration; CRU = clinical research unit; C-SSRS = Columbia-Suicide Severity Rating Scale; ECG = electrocardiogram; GFR = glomerular filtration rate; OATP = organic anion transporting polypeptide; P = predose; PK = pharmacokinetics.

^a Specified times are approximate and actual times will be recorded. Actual sampling time should not exceed 1 hour prior to dosing for the predose sample or $\pm 10\%$ of the specified postdose sample time.

Study Schedule Protocol I8D-MC-AZEB
Period 2

Procedure	Period 2												Discharge/ Follow-up ≥7 days after final dose or ED	Comments	
	Day														
	-1	1	2	3 to 5	6	7	8	9	10	11	12	13			
Outpatient Visit														X	
Subject Discharge from CRU													X		
Weight	X														
C-SSRS	X												X	X	
Physical Exam														X	After screening exam on Period 1 Day -1, exams are to include only medical review and targeted examination, as appropriate.
Pregnancy Test														X	Pregnancy tests will be performed for all females.
Vital Signs (supine and orthostatic) (hours) ^a		P, 4, 8, 12	24				P, 4, 8, 12	24	X	X	X	X		X	Vital signs include blood pressure and pulse rate. Body temperature will be obtained as clinically indicated. Sampling times are relative to the time of study drug administration (0 hour). Additional vital signs may be measured, if clinically indicated.
Clinical Lab Tests						X							X	X	See Appendix 2 for details. Results from sample on Period 1 Day 6 will be reviewed by the investigator prior to dosing on Period 2 Day 1. Tests may be repeated at the investigator’s discretion.
12-lead ECG	X												X	X	Additional ECGs may be obtained if clinically indicated.
Rosuvastatin Administration							X								LY3314814 and rosuvastatin will be co-administered at the same time.

Procedure	Period 2												Discharge/ Follow-up	Comments
	Day													
	-1	1	2	3 to 5	6	7	8	9	10	11	12	13		
LY3314814 Administration		X	X	X	X	X	X	X	X	X	X	X		
Rosuvastatin PK Samples (hours) ^a							P, 1, 2, 3, 4, 5, 6, 8, 12	24	48	72	96	120		Sampling times are relative to the time of rosuvastatin administration (0 hour). Samples may be collected at ED as applicable.
LY3314814 PK Samples (hours) ^a						P, 0.5, 1, 2, 3, 4, 8, 12	P, 0.5, 1, 2, 3, 4, 8, 12	P						Sampling times are relative to the time of LY3314814 administration (0 hour). Samples may be collected at ED as applicable.
Biomarker Samples (hours) ^a							P, 1, 2, 3, 4, 5, 6, 8, 12	24	48	72	96	120		Samples for non-pharmacogenetic biomarker analysis. Sampling times are relative to the time of rosuvastatin administration (0 hour). Samples may be collected at ED as applicable.
AE Assessment	X												X	

Abbreviations: AE = adverse event; CRU = clinical research unit; C-SSRS = Columbia-Suicide Severity Rating Scale; ECG = electrocardiogram; ED = early discontinuation; P = predose; PK = pharmacokinetics.

^a Specified times are approximate and actual times will be recorded. Actual sampling time should not exceed 1 hour prior to dosing for the predose sample or ±10% of the specified postdose sample time.

3. Introduction

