3.2.1.1. Clinical Pharmacokinetic Data

LY3314814 PK have been evaluated following single doses of 1 to 750 mg and at steady state from 15 to 150 mg. Following oral dosing, LY3314814 t_{max} is approximately 1 to 2 hours postdose and then follows a bi-exponential elimination profile. The LY3314814 $t_{1/2}$ is approximately 18 hours. Upon multiple dosing, exposure increases modestly with an accumulation ratio of approximately 1.46, based on area under the drug concentration-time curve (AUC). Steady state appears to be achieved 4 to 8 days following the initiation of dosing, consistent with LY3314814 $t_{1/2}$. Over the dose range from 15 to 150 mg, the AUC of LY3314814 increases in a dose proportional manner, although C_{max} appears to increase in a greater-than-proportional manner (a 3.3-fold increase in dose produced approximately a 4.2-fold increase in $C_{ss,max}$ values). No meaningful differences in PK have been observed between young and elderly healthy subjects, or between healthy subjects and patients with AD. Renal clearance was approximately 1.0 to 1.5 L/h (roughly 5% to 10% of apparent total body clearance), suggesting that renal clearance is a minor elimination pathway. LY3314814 is a substrate of CYP3A, as shown by drug interaction studies where strong inhibitors of CYP3A activity increased LY3314814 exposure by up to 2.85-fold. While LY3314814 was shown to be

a CYP3A inducer in vitro, clinical evidence suggests that there is no meaningful effect of LY3314814 on CYP3A activity. The effect of LY3314814 on Pgp activity has been studied in vitro and clinically. In vitro studies demonstrate that LY3314814 is a substrate and an inhibitor of Pgp. In clinical studies, LY3314814 increased dabigatran exposures by 15% when LY3314814 and dabigatran etexilate were administered at the same time, demonstrating that LY3314814 is a relatively weak inhibitor of Pgp. Since 21 June 2016, a food effect study was completed demonstrating that administration of 50 mg LY3314814 with food resulted in a modest (approximately 17%) reduction in C_{max} , although AUC was not impacted, suggesting that food reduces the rate, but not the extent of absorption. The PK results for the major metabolite AZ13569724 mirrored those of the parent.

Additional information regarding LY3314814 PK may be found in the Investigator's Brochure (IB).

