3.2.1.2. Clinical Safety Data

No clinically significant safety or tolerability concerns have been identified to date in the LY3314814 Phase 1 program up to the highest dose given (750-mg single dose; 150-mg daily dosing for up to 12 days). Across all 10 of the studies completed as of 21 June 2016, 2 serious adverse events (SAEs) were reported in 2 patients (severe ventricular tachycardia in a patient with a previously undisclosed cardiomyopathy, and cellulitis). Both SAEs occurred after 5 days of daily dosing and were judged by the investigator as not related to LY3314814.

The most frequent (occurring in 1% to 10% of healthy subjects) treatment-emergent adverse events (TEAEs) judged by the investigator to be related to study drug during LY3314814 treatment include headache, orthostatic hypotension, dizziness, constipation, back pain, rash, dry skin, lip dry, diarrhea, nausea, dermatitis contact, pruritus, and somnolence. The most common TEAEs judged by the investigator to be related to study drug in patients with mild to moderate AD include blurred vision, headache, and orthostatic hypotension. No clinical laboratory or electrocardiogram (ECG) safety concerns have been identified in the completed Phase 1 studies.

More information about the known and expected benefits, risks, and reasonably anticipated AEs may be found in the IB.

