5.1. Overall Design

This is a Phase 1, open-label, fixed-sequence, 2-period crossover study to evaluate the PK of rosuvastatin administered alone and after 7 days of treatment with LY3314814 in Caucasian healthy male subjects and female subjects not of childbearing potential. [Figure AZEB.1](#) illustrates the study design. All subjects will receive each of the following treatments:

Period 1: single oral dose of 20 mg rosuvastatin on Day 1.

Period 2: oral doses of 50 mg LY3314814 QD on Days 1 to 12 with a single 20-mg rosuvastatin oral dose coadministered on Day 8.

Period 2 will immediately follow Period 1, with no anticipated break between periods. Subjects will reside at the clinical research unit (CRU) for the duration of both study periods.

[figure not shown]

Figure AZEB.1. Illustration of study design for Protocol I8D-MC-AZEB.

Each subject will provide informed consent for study participation and will undergo a screening examination within 45 days prior to enrollment. Subjects who meet all other screening eligibility criteria will return for a second screening visit, at least 21 days prior to enrollment, when samples will be collected for genotype analysis.

In Period 1, subjects will be admitted to the CRU on Day -1. On the morning of Day 1, after an overnight fast of at least 8 hours, a single oral dose of 20 mg rosuvastatin will be administered and will be followed by a fast of at least 4 hours. Blood samples will be collected predose and up to 120 hours postdose (Day 6) for measurement of plasma rosuvastatin concentrations.

There will be a washout period of at least 7 days between the single dose of rosuvastatin on Day 1 in Period 1 and the first dose of LY3314814 on Day 1 in Period 2.

In Period 2, oral doses of 50 mg LY3314814 QD will be taken in the morning of Days 1 to 12. On the morning of Day 7, LY3314814 will be administered after an overnight fast of at least 8 hours and followed by a fast of at least 4 hours. On Day 8, after an overnight fast of at least 8 hours, a single oral dose of 20 mg rosuvastatin will be coadministered with 50 mg LY3314814 and will be followed by a fast of at least 4 hours. On Days 7 and 8, blood samples will be collected predose and up to 24 hours after the LY3314814 dose to determine plasma LY3314814

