6. TREATMENTS

The following is a list of the study treatment names that will be used in the safety TFLs.

Study Treatment Name	Treatment order in TFL
20 mg rosuvastatin (D1)	1
50 mg LY3314814 QD (D1 – D7)	2
50 mg LY3314814 QD + 20 mg rosuvastatin (\geq D8)	3

D = Day

The following is a list of the study treatment names that will be used in the PK TFLs.

Study Treatment Name	Treatment order in TFL
20 mg rosuvastatin	1
50 mg LY3314814 QD + 20 mg rosuvastatin	2
50 mg LY3314814 QD	3

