9.4.4 Vital signs

Vital signs data will be summarized by treatment together with changes from baseline, where baseline is defined as Day 1 predose of each period. Figures of mean vital signs and mean

changes from baseline profiles by treatment will be presented by treatment. Furthermore, values for individual subjects will be listed.

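### The SAP's day-based safety labels report the Day 8 predose vital signs, which are LY3314814 alone after seven doses, as combination, so the LY3314814-alone column holds first-dose data only

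*Protocol*

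**What the plan says.** Protocol 5.1 sets the Period 2 dosing: "oral doses of 50 mg LY3314814 QD on Days 1 to 12 with a single 20-mg rosuvastatin oral dose coadministered on Day 8". In the Schedule of Activities for Period 2, the row "Vital Signs (supine and orthostatic) (hours" has entries on Day 1 (predose, 4, 8, 12 h), Day 2 (24 h), Day 8 (predose, 4, 8, 12 h), Day 9 (24 h), one on each of Days 10 to 13, and one at follow-up. The cells for Days 3 to 7 are empty. The comment on the row adds: "Additional vital signs may be measured, if clinically indicated".

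SAP Section 6 names the safety treatments by day. LY3314814 alone is "50 mg LY3314814 QD (D1 – D7", and the combination is "50 mg LY3314814 QD + 20 mg rosuvastatin (\geq D8", that is, Day 8 onward. SAP 9.4.4 then states: "Vital signs data will be summarized by treatment together with changes from baseline, where baseline is defined as Day 1 predose of each period". Neither document assigns the Day 8 predose reading to LY3314814 alone or uses it as a reference.

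Protocol 3.2.1.1 reports an "accumulation ratio of approximately 1.46" on AUC, with steady state reached after 4 to 8 days. Protocol 3.2.1.2 says the most frequent related events in healthy subjects "include headache, orthostatic hypotension, dizziness".

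**The concern.** One secondary objective is the safety of LY3314814 when coadministered with rosuvastatin, and blood pressure on standing is a natural place to look. A reader of the by-treatment tables and mean-profile figures will set the LY3314814-alone column beside the combination column. Those columns differ in two ways at once: rosuvastatin is added, and LY3314814 moves from first dose to steady state.

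One scheduled reading would show LY3314814 after repeated dosing just before rosuvastatin is added. The day label puts it on the wrong side of the comparison. A worsening in the combination column could then be attributed to coadministration, or dismissed as accumulation, with nothing in the display to separate the two.

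**Working it through.** The plan states no figure for this point, so there is nothing to reproduce. The check assigns each scheduled reading to a SAP label and then sees what the column difference contains.

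**1. Column alignment.** Read by column position, rosuvastatin administration falls on Day 8, and its 24 to 120 h PK samples fall on Days 9 to 13, as Protocol 5.1 requires. The vital-sign row read the same way gives the days listed above.

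**2. Scheduled Period 2 readings under each SAP safety label.**

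| SAP label | Readings | Number | Actual drug state |
|---|---|---|---|
| LY3314814 alone (Days 1-7) | Day 1 predose | 1 | Neither drug; baseline |
| LY3314814 alone (Days 1-7) | Day 1 at 4, 8, 12 h; Day 2 at 24 h | 4 | First LY3314814 dose |
| Combination (Day 8 onward) | Day 8 predose | 1 | LY3314814 alone after seven doses |
| Combination (Day 8 onward) | Day 8 at 4, 8, 12 h; Day 9 at 24 h | 4 | Repeated LY3314814 plus rosuvastatin |
| Combination (Day 8 onward) | Days 10 to 13 | 4 | Repeated LY3314814, rosuvastatin declining |

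The LY3314814-alone label holds 1 + 4 = 5 readings, none after repeated dosing. The combination label holds 1 + 4 + 4 = 9 in-house readings plus follow-up, and one of the nine precedes rosuvastatin.

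**3. Is the Period 2 baseline drug-free?** The washout is at least 7 days (168 h) and the rosuvastatin half-life is about 19 h. The residual is 2^(-168/19) = 0.002, about 0.2%. Yes, in effect.

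**4. Change in LY3314814 exposure between the columns.**
- With the protocol's ratio, first-dose exposure relative to steady state is 1/1.46 = 0.68.
- With a one-compartment model and the stated 18 h half-life, the ratio is 1/(1 - 2^(-24/18)) = 1.66, or 0.60 of steady state. The protocol describes a bi-exponential profile, so this serves only as the other end of a range.
- The half-life implied by 1.46 is 14.4 h. After seven doses the fraction of steady state is 1 - 2^(-168/14.4) = 0.9997, or 1 - 2^(-168/18) = 0.998.

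Exposure therefore rises 1.46- to 1.66-fold between the columns, and Day 8 predose is at steady state either way.

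**5. What each contrast contains.** Let V(d, h) be the reading on day d at hour h, with P for predose.
- Planned combination change: V(8,h) - V(1,P) = [V(8,P) - V(1,P)] + [V(8,h) - V(8,P)]. The first bracket contains no rosuvastatin; it is the shift after seven LY3314814 doses. The second holds the LY3314814 within-day effect, rosuvastatin and time of day.
- Planned LY3314814-alone change: V(1,h) - V(1,P), the first-dose within-day effect and time of day.
- Their difference: predose shift + (steady-state minus first-dose within-day effect) + rosuvastatin.
- Using V(8,h) - V(8,P) instead removes the predose shift only.
- V(8,h) - V(7,h), if Day 7 were measured, would remove both LY3314814 terms.

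**6. A second difference in conditions.** Protocol 6.3.1 requires fasting on Period 2 Days 7 and 8 but not on Day 1, and 3.2.1.1 reports that food lowers LY3314814 Cmax by about 17%. Day 7 is matched to Day 8 on this as well.

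**The case against.** The strongest reply is that the plan never promises this contrast. The endpoint for the safety objective is the incidence of TEAEs and SAEs. Vital signs are supportive, and SAP 9.4.8 rules out inferential safety analysis. Change from Period 2 Day 1 predose fairly describes the total effect under coadministration. All of that stands, and it limits the consequence to interpretation of descriptive tables.

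Safeguards also exist. Protocol 9.4.2 asks for unscheduled orthostatic readings, where possible, during dizziness or posture-related events. Subjects are resident throughout, and adverse events are presented by day of onset. Symptomatic episodes on Days 3 to 7 should therefore be captured. Rosuvastatin alone has its own vital signs in Period 1, and the Day 7 versus Day 8 PK comparison addresses any change in LY3314814 exposure. These reduce the risk of missing a safety problem, but they do not supply scheduled LY3314814-alone vital signs after repeated dosing.

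Three stronger readings are tempting, and the documents do not support them:

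- A reader might infer that the Day 8 predose value is lost. SAP 9.1 calculates change by time point and 9.4.4 lists individual values, so it probably appears in its own row. The table shells are not in the documents. The value would be visible but under the wrong treatment and not used as a reference.
- A reader might infer that a blood-pressure change is inflated by 46%. That assumes effect proportional to AUC. The documents give no vital-sign effect size and no exposure-response relation, and they call the accumulation modest.
- A reader might infer that change from Day 8 predose isolates coadministration. It does not, because LY3314814 is also dosed on Day 8.

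**Conclusion.** The point holds as a misassignment in a descriptive summary. Read literally, the Day 8 onward label reports a pre-rosuvastatin reading as combination. This leaves LY3314814 alone represented by one baseline and four first-dose readings, so the difference between the columns combines a 1.46- to 1.66-fold rise in LY3314814 exposure with the addition of rosuvastatin. The effect on vital signs cannot be quantified from the documents. No primary, inferential or named endpoint result changes.

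The conclusion rests on applying the SAP labels by calendar day as written, on the column reading of the schedule, and on the protocol's accumulation figures. If the unseen table shells already separate Day 8 predose, only the wording and the added reference remain to be settled. The correction is still worth making: it uses a reading already scheduled for every subject, and that reading is the only scheduled one after repeated LY3314814 dosing that precedes the second rosuvastatin dose.

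**What to change.** In SAP 6 and 9.4.4:

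1. Start the combination label at the Day 8 dose, and assign Day 8 predose vital signs to LY3314814 alone (repeated dosing).
2. Label the Day 1-2 values as LY3314814 first dose.
3. Show the Day 8-9 postdose readings as changes from Day 8 predose, in addition to changes from Period 2 Day 1 predose. Add a note that this removes the accumulated predose shift but not the LY3314814 within-day effect.

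The cost is SAP and table-shell wording plus one more change column, with no new data. The SAP was written against the 21 October 2016 protocol and still states 28 subjects where the amended protocol states 42, so it needs updating anyway. Because the SAP was to be signed before first dosing, the change should be recorded as an SAP amendment.

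Optional: for subjects not yet dosed, take vital signs on Day 7 predose and at 4, 8 and 12 h, alongside PK draws already scheduled at those times. This gives a time-matched, fasted reference on the same day the PK analysis uses. It needs a protocol change and four sets of non-invasive readings per subject. Enrollment had begun before Amendment (a), so only some subjects would contribute.
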